5.5.5 Subgroup Analyses

To assess the degree of effect heterogeneity, effect modifier analyses are proposed, on the ITT analysis set, for the primary efficacy endpoint and the key secondary efficacy endpoint of $\geq 50\%$ reduction in TSC-associated seizure frequency.

For the primary efficacy endpoint, the effect modifier analysis will be performed using the negative binomial regression analysis as described in Section 5.5.2. The model will be updated to include covariates for each level of the effect being tested (excluding a reference level), individually and with interactions with time, interactions with treatment arm and interactions with time and treatment. A separate model will be used for testing each effect. The treatment ratios (GWP42003-P vs. placebo), percent reduction and 95% confidence intervals will be presented for each level of the effect. In addition, the effect by time by treatment arm interaction p-value, testing the hypothesis that the effect level treatment ratios are homogeneous, will be presented.

For the key secondary efficacy endpoint of $\geq 50\%$ reduction in TSC-associated seizure frequency, patients with a $\geq 50\%$ reduction in seizure frequency will be modelled using logistic regression, including stratified age group and treatment arm as covariates. The model will also include covariates for each level of the effect being tested (excluding a reference level), individually and with interactions with treatment arm. A separate model will be used for testing each effect. The number and percent of responders, and odds ratios and 95% confidence intervals will be presented for each level of the effect. In addition, the effect by treatment arm interaction p-value, testing the hypothesis that the effect level odds ratios are homogeneous, will be presented.

The following effects will be tested:

- Age group (1-6 years, 7-11 years, 12-17 years and 18-65 years). Note: stratified age group will be removed as a covariate for this model.
- Sex (Male, Female).
- Region (US, Rest of the World).
- Clobazam use (Yes, No).
- Valproic acid use (Yes, No).
- . Levetiracetam use (Yes, No).
- Vigabatrin use (Yes, No).
- Baseline average TSC-associated seizures per 28 days (\leq observed Tertile 1, $>$ observed Tertile 1 to \leq observed Tertile 2, $>$ observed Tertile 2). The observed tertile values will be rounded to the nearest whole number.
- Number of concurrent AEDs (<3 , ≥ 3).
- Number of prior AEDs (<5 , ≥ 5).
- Number of prior and concurrent AEDs (<8 , ≥ 8).

Effects of patients taking other AED types will also be tested if the overall frequency of patients taking the AED is $>25\%$.

5.6 Safety Evaluation

5.6.1 Exposure to IMP

Blinded Phase:

Patients are required to take IMP twice daily (morning and evening). The first dose will be taken in the clinic on Day 1. The date of final dose in the treatment phase will be recorded on the CRF. The date of final dose, for patients who enter the taper period, will be recorded on the CRF at the end of taper visit.

The total number of dosing days in the treatment phase will be calculated as:

$$(\text{Date of last dose in the treatment phase} - \text{Date of Day 1}) + 1$$

The date of last dose in the treatment phase will be obtained from the CRF at the end of treatment visit.

Any missed doses during treatment should be recorded on the 'IMP Missed Doses Log' CRF page. The number of days with any missed doses and the number of days where trial medication was not taken in the AM nor PM will be summarized based on data in the treatment phase (Day 1 to end of treatment visit).

In addition, the number of days in which trial medication was taken at least once (AM or PM) will be summarized and calculated as:

$$\text{Total number of dosing days} - \text{the number of days where trial medication was not taken in the AM nor PM}$$

The number of days in which trial medication was taken both AM and PM will be summarized and calculated as:

$$\text{Total number of dosing days} - \text{the number of days with any missed doses}$$

The above summaries will be presented for all patients and repeated for patients who completed the treatment phase.

In addition, the expected daily volume of IMP to be administered during the treatment phase, once a patient has titrated to target dose, will be summarized by treatment.

The expected daily volume of IMP will be calculated as:

$$2 \times [\text{Weight (kg) at Day 1} \div 8 \text{ and rounded to the nearest } 0.1]$$

for patients randomized to the 25 mg/kg/day dose level and:

$$2 \times [\text{Weight (kg) at Day 1} \div 4 \text{ and rounded to the nearest } 0.1]$$

for patients randomized to the 50 mg/kg/day dose level.

Finally, IMP compliance will be summarized by treatment and calculated as:

$$100 \times (\text{Number of days IMP taken at least once} + \text{number of days IMP taken both AM and PM}) \div (2 \times \text{day of completion or withdrawal during the treatment period})$$

Open-label Extension:

The total number of dosing days will be calculated for the OLE and presented along with a categorical summary of patients whose largest dose was 25 mg/kg/day or less and patients whose largest dose was over 25 mg/kg/day during the OLE treatment phase.

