2.3.3 Robustness to Withdrawn Patients

There were higher proportions of patients in each treatment arm that withdrew during the blinded phase treatment period when compared with placebo. In order to assess the robustness of the results, 2 analyses in the following sections are proposed.

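### In SAP Section 5.6.1, dosing days stop at the last dose but missed days run to the end of treatment visit, so any missed doses logged in between are deducted from a total that never held them

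*SAP*

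**What the plan says.** SAP Section 5.6.1 defines four linked quantities for the blinded phase.

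- **Total dosing days**: date of last dose in the treatment phase minus date of Day 1, plus one. On the source of the end date, "The date of last dose in the treatment phase will be obtained from the CRF at the end of treatment visit".
- **Missed days**: "Any missed doses during treatment should be recorded on the 'IMP Missed Doses Log' CRF page". Two counts are taken from that log, days with any missed dose and days with neither dose taken. Both "will be summarized based on data in the treatment phase (Day 1 to end of treatment visit").
- **Days taken**: days with at least one dose are total dosing days minus days with neither dose. Days with both doses are total dosing days minus days with any missed dose.
- **Compliance**: 100 times the sum of the two days-taken counts, divided by twice the "day of completion or withdrawal during the treatment period".

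No sentence limits the missed days to those up to the last dose, and none sets a floor for the result. The SAP also does not say whether doses not taken after a permanent stop are entered in the log.

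**The concern.** A subtraction of missed days from dosing days makes sense only if both are counted over the same interval. Here the first interval ends at the last dose and the second at a visit that may come later. A logged missed day in the gap is absent from total dosing days and is then subtracted from them as well. The compliance denominator also covers the gap, so the patient is charged twice for one day off drug.

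The quantities at stake are the days-taken counts and the compliance percentage in the exposure and compliance tables (Tables 10.1 and 7.1 in Appendix 6). The patients exposed to the problem are those who stop the study drug some time before their end of treatment visit. If sites differ in whether they log doses after a stop, two patients with the same dosing history would receive different compliance values.

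**Working it through.** The SAP gives no compliance or exposure figure to reproduce, so the check applies its formulas directly.

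**Inputs**
- L = day of last dose, which equals total dosing days (Section 5.6.1).
- V = day of the end of treatment visit, scheduled for Day 113 (Table 2). It can be earlier for a patient who withdraws.
- g = V − L, the number of days between the last dose and the visit.
- Assumption: V is also the day of completion or withdrawal. Section 5.6.1 does not state this.
- For simplicity, no dose is missed up to Day L.

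**If all g days are logged as missed**
- Days with at least one dose = L − g.
- Days with both doses = L − g.
- Compliance = 100 × 2(L − g) / (2V) = 100 × (L − g)/(L + g).

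**If missed days are cut off at the last dose, or none are logged after it**
- Both days-taken counts = L.
- Compliance = 100 × L/(L + g).

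The shortfall is therefore 100 × g/(L + g) percentage points.

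| L | g | V | Gap days logged, formula as written | Missed days cut at last dose | Shortfall (points) |
|---|---|---|---|---|---|
| 113 | 0 | 113 | 113/113 = 100.0% | 113/113 = 100.0% | 0 |
| 112 | 1 | 113 | 111/113 = 98.2% | 112/113 = 99.1% | 0.9 |
| 106 | 7 | 113 | 99/113 = 87.6% | 106/113 = 93.8% | 6.2 |
| 100 | 13 | 113 | 87/113 = 77.0% | 100/113 = 88.5% | 11.5 |
| 60 | 7 | 67 | 53/67 = 79.1% | 60/67 = 89.6% | 10.4 |
| 30 | 7 | 37 | 23/37 = 62.2% | 30/37 = 81.1% | 18.9 |

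**When the result turns negative.** L − g < 0 requires the gap to exceed the dosing days, that is V > 2L. With V = 113 this means a last dose on Day 56 or earlier, with every later day up to the visit logged as missed: (56 − 57)/113 = −0.9%. That is an extreme case.

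**Missed days up to the last dose.** These lie inside total dosing days and are deducted once, as they should be. The two windows differ only after Day L.

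**Comparison within the document.** Section 2.4.1 of the SAP addendum, on doses received, ends its period at the earlier of the last blinded-phase dose and Day 113. Section 5.6.1 lacks such a cut-off for its missed-day counts.

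**The case against.** The strongest reply is that the log is for doses missed during treatment, and a dose not taken after the drug has been stopped for good is not naturally a missed dose of that kind. On that reading the log holds nothing after Day L, and the formulas give L/(L + g), the right answer. The mention of the end of treatment visit may serve only to keep taper-period entries out, since Section 5.6.1 records the final taper dose separately. This stands as far as it goes: the error is conditional. It does not remove the point, because the written window runs to the visit, nothing in the SAP excludes log entries after the last dose, and a programmer following the text would count any that exist.

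Two stronger readings are tempting. A reader might infer that early stoppers will show negative compliance. That needs a gap longer than the dosing period, and the SAP does not say how long after the last dose the visit takes place. A reader might also infer that adherence on active drug will look worse than it was, because Section 2.3.3 of the addendum reports: "There were higher proportions of patients in each treatment arm that withdrew during the blinded phase treatment period when compared with placebo". More withdrawals in the active arms make a difference between arms possible. They do not show it, since the bias also needs a gap between last dose and visit and log entries within that gap, and the SAP reports neither.

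The reach is also limited. No hypothesis test uses these variables, and Section 5.2.3 does not tie per-protocol exclusion to the compliance percentage.

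**Conclusion.** The mismatch of windows is on the face of Section 5.6.1. Where missed doses are logged between the last dose and the end of treatment visit, the days-taken counts are too low by g days and compliance is too low by 100 × g/(L + g) points. For g up to 13 days in the cases shown, that is 0.9 to 18.9 points for an individual patient. The compliance figure rests on the visit day being the day of completion or withdrawal and on every gap day being logged. Where none is logged, or where dosing continues to the visit, there is no error. How many patients are affected cannot be told from the SAP. Efficacy results are untouched. Severity is minor: a stated rule that can give a wrong descriptive figure, with no demonstrated bias between arms.

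**What to change.** Add one sentence to Section 5.6.1: in deriving days with at least one dose, days with both doses, and compliance, missed-dose days are counted only from Day 1 to the date of last dose in the treatment phase. Leave the compliance denominator unchanged, so that stopping early still lowers compliance, but only once.

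The cost is that sentence and one date condition in the program. Results do not change for patients with no log entries after the last dose. For the others, the double deduction and any negative values disappear.

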5.6.2 Adverse Events

All reported AEs will be classified by system organ class (SOC), preferred term and lower level term using Version 19.1 of MedDRA.

Summaries will be presented by treatment arm as well as SOC and preferred term.

A blinded phase treatment emergent AE (TEAE) is defined as an AE with a start date on or after the first dose of IMP during the blinded phase up to and including the date of first dose of the OLE phase (OLE Day 1). An OLE phase TEAE is defined as an AE with a start date on or after the OLE Day 1. If an AE has a partial start date and it is unclear from the partial date (or the stop date) whether the AE started prior to or post first dose of IMP then the AE will be considered treatment emergent and if it is unclear which phase the event started, it will be assigned to both phases. If the start date of the AE is the same as the date of first dose of IMP from the blinded phase and the plausible relationship to IMP is marked on the CRF as "Prior to study medication" then the AE will not be considered treatment emergent.

An AE will be considered treatment-related if the plausibility relationship to trial medication is recorded on the CRF as 'yes'. If the data on plausibility relationship to trial medication is missing then the AE will be considered treatment-related.

An AE will be considered leading to permanent discontinuation of IMP if the action taken with IMP is recorded on the CRF as 'study medication stopped' or the outcome is recorded on the CRF as 'patient died'.

An AE will be considered leading to IMP dose reduction excluding permanent discontinuation if the action taken with IMP is recorded on the CRF as 'dose reduced', 'dose reduced temporarily' or 'study medication interrupted'.

An AE will be considered leading to temporary IMP dose reduction if the action taken with IMP is recorded on the CRF as 'dose reduced temporarily'.

An AE will be considered leading to permanent IMP dose reduction excluding permanent discontinuation if the action taken with IMP is recorded on the CRF as 'dose reduced'.

An AE will be considered fatal if the outcome is recorded on the CRF as 'patient died'.

The following summaries will be generated separately for the blinded and OLE phase (counts are by patient unless specified otherwise):

- Overall summary of AEs, including number of patients reporting each of; TEAEs, treatment related TEAEs, TEAEs leading to withdrawal, treatment related TEAEs leading to withdrawal, serious TEAEs, treatment related serious TEAEs.
- Summary of TEAEs.
- Summary of TEAEs by event.
- Summary of treatment-related TEAEs.
- Summary of treatment-related TEAEs by event.
- Summary of TEAEs by maximal severity.
- Summary of TEAEs by sex.
- Summary of serious TEAEs.
- Summary of serious TEAEs by event.
- Summary of non-serious TEAEs.
- Summary of non-serious TEAEs by event.
- Summary of treatment-related serious TEAEs.
- Summary of treatment-related serious TEAEs by event.
- Summary of TEAEs leading to permanent discontinuation of IMP.

- Summary of treatment-related TEAEs leading to permanent discontinuation of IMP.
- Summary of TEAEs leading to IMP dose reduction excluding permanent discontinuation (by resolution and overall).
- Summary of treatment-related TEAEs leading to IMP dose reduction excluding permanent discontinuation (by resolution and overall).
- Summary of TEAEs leading to temporary IMP dose reduction (by resolution and overall).
- Summary of treatment-related TEAEs leading to temporary IMP dose reduction (by resolution and overall).
- Summary of TEAEs leading to permanent IMP dose reduction excluding permanent discontinuation (by resolution and overall).
- Summary of treatment-related TEAEs leading to permanent IMP dose reduction excluding permanent discontinuation (by resolution and overall).
- Summary of fatal TEAEs.
- Summary of TEAEs by time of first onset of AE.
- Summary of TEAEs by time to AE resolution.
- Summary of TEAEs reported in $\geq 2\%$ of patients (after rounding) in the GWP42003-P treatment arms and where the incidence is greater than the placebo treatment arm.
- List of patients experiencing TEAEs by SOC and preferred term.
- Summary of pre-treatment AEs (blinded phase only).

For the summary of TEAEs by maximal severity, for each patient, the worst severity recorded by preferred term, SOC and overall will be used for summary purposes. If severity is missing, the worst case (severe) will be assumed.

For summaries by resolution, AEs with an outcome of 'recovered' or 'recovered with sequelae' will be summarized as 'Resolved' and AEs with an outcome of 'continuing', 'patient died' or those with a missing outcome will be summarized as 'Not resolved'.

For the summary of TEAEs by time of first onset of AE, data will be summarized under the following categories:

- Weeks 1 to 2 (Day 1 to 14).
- Weeks 3 to 4 (Day 15 to 28).
- Weeks 5 to 8 (Day 29 to 56).
- Weeks 9 to 12 (Day 57 to 84).
- >12 weeks (> Day 84).

The time to first onset of AE will be calculated for TEAEs as:

$$\text{Start date of AE} - \text{Date of first dose of IMP} + 1$$

If patients have multiple occurrences of an AE then the AE will be counted once for the first occurrence only. Percentages will be based on the number of patients in the safety analysis set who have a visit or follow-up call within each time period above.

For the summary of TEAEs by time to AE resolution, data will be summarized under the following categories:

- 1 week (≤ 7 days).
- 2 weeks (8 to 14 days).
- 3 weeks (15 to 21 days).
- 4 weeks (22 to 28 days).
- >4 weeks (>28 days).
- Ongoing (for AEs not resolved).

The time to AE resolution will be calculated for TEAEs as:

$$\text{Stop date of AE} - \text{Start date of AE} + 1$$

If patients have multiple occurrences of an AE then the AE will be counted once for the occurrence with the longest time to AE resolution. However, if any of the AEs are not resolved then the AE will be counted once within the 'Ongoing' category.

The start and stop day of the AE relative to the first dose of IMP (as recorded on the CRF) will be calculated as per Section 5.1.2. For partial dates, if it is clear from the partial date that the start/stop day was prior to the first dose of IMP, then 'pre' will be listed, similarly if it is clear that the event was post the first dose of IMP then 'post' will be listed as the start/stop day as appropriate.

All AEs will be listed. Listings will include the start and stop day of the AE, a flag for treatment emergence, and limited demographic information about the patient (age, sex, race and weight at screening). A separate listing will be provided for pre-treatment AEs, serious AEs and events of special interest (see Appendix 1).

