3. INVESTIGATIONAL PLAN

3.1 Trial Design

This multicenter trial consists of a randomized, placebo-controlled, double-blind phase followed by an open-label extension (OLE) phase.

Blinded Phase:

The blinded phase of the trial is a randomized, double-blind, parallel-group, 16-week comparison of two doses of GWP42003-P vs. placebo. Patients will complete a 1-week screening period and a 4-week baseline period before they are randomized to receive either 25 mg/kg/day GWP42003-P, 50 mg/kg/day GWP42003 P or placebo. Randomization will be stratified by age according to the following ranges: 1–6, 7–11, 12–17 years and 18–65 years. Patients will begin a 4-week dose escalation period, titrating up to their assigned dose, before continuing on a stable dose of blinded Investigational Medicinal Product (IMP) for 12 weeks.

Dose escalation for each patient is subject to the investigator's assessment of safety and tolerability. If a dose becomes poorly tolerated, the investigator may consider temporarily or permanently reducing the dose for the remainder of the trial.

Following completion of the blinded phase, patients will be invited to continue to receive GWP42003-P in an OLE.

Those patients opting not to enter the OLE will complete a 10-day taper period (down-titrating 10% per day for 10 days).

Open-label Extension Transition:

In order to maintain consistent exposure to IMP and maintain the integrity of the blind, patients will enter a 2-week blinded transition to the OLE. OLE IMP will be titrated up to 25 mg/kg/day whilst blinded IMP is simultaneously tapered down to zero. All patients will complete the transition and enter the OLE taking 25 mg/kg/day GWP42003-P:

- Patients from the placebo arm will titrate up to 25 mg/kg/day GWP42003-P.
- Patients from the 25 mg/kg/day GWP42003-P arm will continue to take 25 mg/kg/day GWP42003-P.
- Patients from the 50 mg/kg/day GWP42003-P arm will taper down (10% per day) to 25 mg/kg/day GWP42003-P.

Open-label Extension:

The OLE consists of a 3-week titration period followed by a maintenance period and a 10-day taper period. The initial OLE period will last for a maximum of 1 year.

Following titration according to the titration schedule, patients will continue with their optimal GWP42003-P dose. However, investigators may decrease the dose if a patient experiences intolerance, or increase the dose to a maximum of 50 mg/kg/day if required for better seizure control, until the optimal dose is found.

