5. STATISTICAL METHODS

5.1 General Considerations

In all tables, listings and figures for the double-blind phase, the trial medications will be referred to and labelled as per Table 1.

Table 1 Blinded Phase Trial Treatments

Endpoint	Actual Treatment	Treatment Label
Efficacy	Pooled Placebo	Placebo
Safety	25 mg/kg/day Placebo	Placebo 25 mg/kg
	50 mg/kg/day Placebo	Placebo 50 mg/kg
All	25 mg/kg/day GWP42003-P	25 mg/kg
All	50 mg/kg/day GWP42003-P	50 mg/kg

For safety tables where placebo is split by dosing volume, an additional Pooled Placebo column will be included.

For OLE tables, columns will be included for treatment received during the double-blind phase (GWP42003-P or placebo, i.e. not split by dose) and overall.

In all tables, listings and figures, the trial visits will be referred to and labelled as per Table 2.

Table 2 Trial Visits

Actual Visit	Visit Label
Visit 1: Screening	Day -35
Visit 2: Day -28, baseline visit	Day -28
Visit 3: Day 1, Randomization	Day 1
Visit 4: Day 15	Day 15
Visit 5: Day 29	Day 29
Visit 6: Day 43	Day 43
Visit 7: Day 57	Day 57
Visit 8: Day 71, Telephone	Day 71
Visit 9: Day 85	Day 85
Visit 10: Day 113	End of Treatment
Visit 11: Day 123	End of Taper
Visit 12: Day 151	Safety Follow-Up
Visit B1: Day 1, Enrollment	OLE Day 1
Visit B2: Day 15	OLE Day 15
Visit B3: Day 36	OLE Day 36
Visit B4: Day 92	OLE Day 92
Visit B5: Day 141, Re-stocking of supplies	OLE Day 141
Visit B6: Day 183	OLE Day 183
Visit B7: Day 232, Re-stocking of supplies	OLE Day 232
Visit B8: Day 274	OLE Day 274
Visit B9: Day 323, Re-stocking of supplies	OLE Day 323
Visit B10: Day 365	OLE End of Treatment
Visit B11: Day 375	OLE End of Taper
Visit B12: Day 389	OLE Post-taper Safety Telephone Call
Day 403	OLE Follow-Up

Unless stated otherwise, continuous variables will be summarized showing the number of non-missing values (n), mean, standard deviation, median, minimum and maximum and categorical variables will be summarized showing the number and percentage of patients falling in each category. For continuous summaries of seizure frequency, the lower and upper quartiles will also be presented.

Minimum and maximum values will be presented to the same decimal precision as the raw data. Mean and median will be presented to one more decimal place than the raw data, and standard deviation to 2 more decimal places than the raw data. Percentages will be presented to one decimal place.

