5.1.2 Day Numbering

Blinded Phase:

The first day of treatment (Day 1) will be taken from the Study Medication case report form (CRF) page at Visit 3. However, if this date is missing then the date of Visit 3 will be used.

Any days prior to Day 1 will be numbered relative to this day and calculated as:

Date - (Date of Day 1); to give Day -1, -2, -3 etc.

Any days post Day 1 will be calculated as:

1 + Date - (Date of Day 1)

Open-label Extension:

The first day of treatment in the OLE (OLE Day 1) will be day of entry into the OLE, which is expected to be the same day as the end of treatment visit from the blinded phase. OLE day will be calculated as above but relative to OLE Day 1.

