5.1.3.4 Treatment Period

The treatment period of the double-blind phase is defined as Day 1 to Day 113.

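### The blinded-phase TEAE window closes only at OLE Day 1, so patients who never enter the OLE add taper and off-drug events to the by-arm tables, and OLE Day 1 events count in both phases

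*SAP*

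**What the plan says.** SAP Section 5.6.2 defines a blinded-phase TEAE as "an AE with a start date on or after the first dose of IMP during the blinded phase", running "up to and including the date of first dose of the OLE phase (OLE Day 1". For the extension, "An OLE phase TEAE is defined as an AE with a start date on or after the OLE Day 1". Section 5.1.2 places OLE Day 1 on the day of entry into the OLE, "which is expected to be the same day as the end of treatment visit from the blinded phase", which Table 2 schedules at Day 113.

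Entry is optional and is offered after completion. Section 3.1 says: "Those patients opting not to enter the OLE will complete a 10-day taper period". Table 2 puts the end of that taper at Day 123 and the safety follow-up at "Visit 12: Day 151". Entrants taper their blinded medication after OLE Day 1, during the two-week transition.

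For efficacy the phase has a fixed length: "The treatment period of the double-blind phase is defined as Day 1 to Day 113" (Section 5.1.3.4). The TEAE definition does not use it. The onset table in Section 5.6.2 ends with a row for more than 12 weeks (after Day 84) that has no upper limit.

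Addendum Section 2.3.3 reports: "There were higher proportions of patients in each treatment arm that withdrew during the blinded phase treatment period when compared with placebo".

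**The concern.** Tables 11.1 to 11.14 and 12.1 to 12.13 set crude patient percentages side by side by arm. The period over which a patient can contribute depends on whether that patient enters the OLE, which is decided after randomization. A taper or post-taper event in a non-entrant counts as a blinded-phase TEAE under the assigned dose. A later event of the same kind in an entrant is an OLE TEAE only, in columns that are not split by dose. Withdrawal was more frequent in both active arms, so the mix of on-treatment and later events can differ by arm.

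This matters most for terms such as drug withdrawal syndrome and rebound effect, which Appendix 1 lists as being of special interest, because the phase of treatment decides how such an event is read. In the onset table, the last row covers Days 85 to 113 for entrants and Days 85 to 151 for decliners, and it can also include withdrawn patients already off drug.

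The shared boundary day adds a smaller fault. An event that follows a former placebo patient's first active dose on OLE Day 1 is counted against placebo as well as in the OLE.

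**Working it through.** The SAP gives no figure for this point, so there is none to reproduce. The check is of the definition, followed by day arithmetic and an illustration.

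**1. Is there another end date?** Section 5.6.2 names only OLE Day 1. The imputation rules in Section 5.1.1.3 set no window, and the last onset row is open. No rule based on last dose, end of taper, Day 113 or Day 151 appears for AEs.

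**2. Scheduled days (Table 2).**
- Entrant: Day 1 to Day 113 = 113 days.
- Completer who declines: Day 1 to Day 151 = 151 days.
- Difference: 151 − 113 = 38 days, and 38/113 = 34%. Of these, 123 − 113 = 10 are on a tapering dose and 151 − 123 = 28 are off drug.

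**3. Withdrawals.** Assume the same 38-day tail after withdrawal on day w, so the window is w + 38 and the share after treatment is 38/(w + 38).

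| Withdrawal day | Window (days) | Share after treatment |
|---|---|---|
| 29 | 67 | 57% |
| 57 | 95 | 40% |
| 85 | 123 | 31% |

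The window equals an entrant's when w = 113 − 38 = 75. If withdrawals are uniform over Days 1 to 113, 74/113 = 65% fall before that day and the mean window is 57 + 38 = 95 days. Most withdrawals are therefore observed for less total time than an entrant, but a large part of that time is after treatment.

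**4. Arm level: observation time.** Assume 15% withdrawn in an active arm and 5% in placebo, with 2% of completers declining in each. The mean window among completers is 0.98 × 113 + 0.02 × 151 = 113.76 days.
- Active: 0.15 × 95 + 0.85 × 113.76 = 110.9 days. Time after treatment is 38 × (0.15 + 0.85 × 0.02) = 6.35 days, or 5.7%.
- Placebo: 0.05 × 95 + 0.95 × 113.76 = 112.8 days. Time after treatment is 38 × (0.05 + 0.95 × 0.02) = 2.62 days, or 2.3%.

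Counting only the 28 off-drug days (multiply by 28/38), the shares are 4.2% and 1.7%.

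**5. Arm level: incidence.** Let p be the incidence over 113 days under a constant hazard. The gain per non-entrant from 38 more days is (1 − p) × [1 − (1 − p)^(38/113)]. This is 3.13 points at p = 10% and 7.91 at p = 30%. Multiply by the assumed difference in non-entry:

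| Non-entry, active vs placebo | p = 10% | p = 30% |
|---|---|---|
| 5% vs 0% | 0.16 | 0.40 |
| 15% vs 5% | 0.31 | 0.79 |
| 30% vs 5% | 0.78 | 1.98 |

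Entries are percentage points added to the arm difference. At p = 2% the range is 0.03 to 0.17. The formula gives every non-entrant a full 113 days on treatment. An early withdrawal gains somewhat more, at most 1 − 0.7^(38/113) = 11.3 points at p = 30%. With the same mix in both arms, that caps the bottom-right cell at 0.113 × 25 = 2.8.

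**6. The 2% table.** With 70 patients per arm (Section 3.2), one patient is 1.4% (rounds to 1%) and two are 2.9% (rounds to 3%). A single post-treatment event can therefore carry a preferred term over the rounded 2% threshold of Table 11.8.

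**The case against.** The strongest reply is that this is a wording gap with little practical effect. The AE tables are descriptive and no AE hypothesis test is planned. The shifts above are mostly below one point. AE collection presumably stops near the Day 151 visit, and the protocol may say so. Keeping events after the last dose is a common conservative convention, and taper days are still dosing days. Listings carry start and stop days, and Section 5.6.1 records both the last treatment-phase dose and the last taper dose, so any event can be placed. The overlap is one calendar day, in a section that already assigns events of unclear phase to both phases.

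Much of this stands. The effect is small, taper is not off-drug time, and events can be separated at listing level. It does not remove the defect. A collection limit in the protocol would cap the tail but would not make the analysis window the same for entrants and non-entrants. A post-dose convention is defensible when it is stated and applied to everyone, whereas here it applies only to patients without an OLE Day 1. The by-arm tables do not show which events came after treatment. The both-phases provision concerns partial dates; the boundary-day overlap applies even when onset is known to follow the first OLE dose.

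**Conclusion.** The definition needs correcting, but the likely effect on the results is modest. As written, blinded-phase TEAEs include taper and off-drug events for patients who do not enter the OLE and exclude later events for those who do, and OLE Day 1 is counted in both phases. The arm-level shift is about 0.2 to 2 percentage points for events with 10% to 30% incidence. That rests on assumed non-entry rates, a constant hazard and a 38-day tail for every non-entrant, and it would be larger if taper itself provokes events.

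A reader might infer three stronger things that the SAP does not support:
- **That active-arm patients are observed longer.** The 34% applies only to completers who decline. In the 15% versus 5% withdrawal example, the active arm's mean window is slightly shorter (110.9 against 112.8 days).
- **That declining the OLE differs by arm.** The addendum speaks only of withdrawal, and the SAP gives no arm rates for either.
- **That the AE comparison is seriously distorted.** Nothing in the SAP shows a shift of that size.

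**What to change.** In Section 5.6.2, define for the arm comparison one on-treatment window for every patient: from first dose to the last treatment-phase dose recorded on the CRF (Section 5.6.1). Count an event on OLE Day 1 as blinded-phase only if its onset precedes the first OLE dose, and say what happens when the order is unknown. Tabulate later-onset AEs in patients who do not enter the OLE in a separate by-arm table, split into taper and post-taper follow-up. Keep the current all-events count as a supportive table.

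The cut should be the patient's own last treatment-phase dose rather than Day 113. Under the uniform-withdrawal assumption, the average part of the 38-day tail that falls on or before Day 113 is (75 × 38 + 703)/113 = 31.4 days, where 703 is the sum of 37 down to 0. A Day 113 cut would therefore leave 83% of withdrawals' tail time in the main table.

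The cost is a few sentences and one or two extra tables, with no new data and no events lost. Blinded-phase TEAE counts in the main table fall slightly, and withdrawn patients contribute less time to it, which is why the supportive table should stay. If the blinded-phase outputs already exist, the new tables can be added and labelled post hoc.
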